4.3.1 Demographic Data and Other Baseline Characteristics

Source: DMT002, DML002, VST003, VSL003, NSL016

Patient distribution, demographic and baseline characteristics will be presented using descriptive statistics. The number and percentage of patients receiving concomitant medications will be presented in frequency tables according to the ATC classification and the generic name. The number of patients with prior medical conditions will be presented. Information on dosage, including daily doses, exposure time and the total dose, will be presented using descriptive

statistics for each treatment group, additionally baseline characteristics will be presented for subgroups (patients with IBS and other functional bowel diseases, patients with constipation, diarrhea, both constipation and diarrhea, neither of them)

All variables in this section will be reported on a by-subject data listing.

Such continuous characteristics as: age, height, weight, body mass index (BMI), body temperature, respiration rate, systolic blood pressure (in sitting position) (SBP), diastolic blood pressure (in sitting position) (DBP), pulse rate will be reported on tables grouped by treatment with the number (n), arithmetic mean, standard deviation (SD), median, minimum (min) and maximum (max) of unique subjects who have at least one measurement of the demographic data or other baseline characteristics.

For more detailed information about values calculations see Module 2

4.3.2 Medical History

Source: MHT001, MHL001, MHL002, NSL001, NST006

Medical history will be presented in tables grouped by treatment, SOCs, HLTs, PTs and sorted by descending order of total incidence. SOCs, HLTs, PTs will be coded by the Medical Dictionary for Regulatory Activities version 24.0 ENG (MedDRA 24.0 ENG). In addition to this, the information will be reported on a by-subject data listing, for more detailed information see Module 2.

Additionally, the listing for disease information (index diagnosis and start date) and frequency table by index diagnosis will be presented.

An intergroup comparison for two treatment groups is not planned.

4.3.3 Physical Examinations

Source: NSL002

Physical examinations will be reported on a by-subject data listing with the visits, visit dates of physical examinations.

4.3.4 Vital Signs, height and weight

Source: VST001, VST002, VSL004, VSL005

All variables in this section will be reported on a by-subject data listing.

All characteristics will be reported on tables grouped by treatment with the number (n), mean, standard deviation (SD), median, minimum (min) and maximum (max) of unique subjects who have at least one measurement of the vital signs (other baseline characteristics).

Also, abnormal vital signs from the module 1 and markedly abnormal vital signs criteria will be reported on table grouped by treatment with the number (n) and percentage (%) of unique subjects with at least one type of measurement of the parameter.

For more detailed information about norms, value calculation etc. see Module 2.

4.3.5 Visual Analogue Scales

Source: NST002, NSL003, NSL014, NSL015

The results of assessment by visual analogue scales (NRS-11) at screening/run-in and study treatment periods will be presented in by-subject data listing with the name of a scale, time of assessment, units and result of assessment and summarized by treatment group and scale. The number (n), mean, standard deviation (SD), median, minimum (min) and maximum (max) of unique subjects with at least one scale measurement will be presented in the table.

4.3.6 Safety Laboratory Data

Source: LBT001, LBT002, LBT003, LBT004, LBT005, LBL002, LBL003, LBL007, LBL008

All variables in this section will be reported on a by-subject data listings.

Safety laboratory information will be collected as quantitative (hematology and biochemistry assessments only) and qualitative (all laboratory tests) data. The quantitative data will be reported on listings and tables with the following statistics: the number (n), arithmetic mean, standard deviation (SD), median, minimum (min) and maximum (max) of unique subjects who have at least one measurement of safety laboratory data. In contrast to this, the qualitative data will be reported on shift-tables with the following statistics: the number (n) and percentage (%) of unique subjects with safety laboratory measurement. There are will be presented such characteristics of values as "Low", "Normal" and "High".

Each center uses its own safety laboratory norms for hematology and biochemistry assessments and normal values for urinalysis are not defined centrally. Investigators will choose the most appropriate answer ("Normal" or "Abnormal") for a value. In case an investigator chooses the point "Abnormal" he/she has to define whether the deviation is clinically significant ("Yes" or "No").

For more detailed information see Module 2.

4.3.7 Adverse Events

Source: AET001, AET002, AET003, AET005, AET006, AET007, AET008, AET009, AET010, AEL002, AEL008, AEL009, AEL010, AEL011, AEL012, AEL013

Adverse Events will be presented in tables grouped by treatment, SOCs, HLTs, PTs and sorted by descending order of total incidence. SOCs, HLTs, PTs will be coded by the Medical Dictionary for Regulatory Activities version 23.1 ENG (MedDRA 23.1 ENG). In addition to this, the information will be reported on a by-subject data listing.

Adverse Events (TEAEs) started after the last administration of study drug but within the Gap Period after the last administration will also be attributed to the Treatment Period. For more detailed information see Module 2.

An intergroup comparison for two treatment groups is not planned.

4.3.8 Time of administration (patient diary)

Source: NSL004

Time of administration collected in patient diary will be presented in a by-subject data listing with the date and treatment day of assessment and also time of each administration per day.

4.3.9 Concomitant Medication

Source: CMT001, CML001, CML002

Concomitant Medication will be presented in tables grouped by treatment, ATC 3rd level or ATC 4th level, preferred name WHO DD and sorted by descending order of total incidence. All parameters except treatment group will be coded by the World Health Organization-Drug Dictionary (WHO-DD) of the latest version. In addition to this, the information will be reported on a by-subject data listing.

Medications started after the last administration of study drug but within the Gap Period (7 days) after the last administration will also be assigned to the Treatment Period. For more detailed information see Module 2.

An intergroup comparison for two treatment groups is not planned.

4.3.10 Drug Accountability, Treatment Compliance and Exposure

Source: DAT001, DAL001, NST005, NSL04

The patient should take the first study drug dose at the Visit 2 day (Week 0). During telephone contact (TC 1, Week 2, Day 0), the Investigator checks the patient's treatment compliance and whether he/she follows the recommendations on the Patient's Diary filling, and, if necessary, conducts an additional conversation with the patient about the proper drug administration and filling out the Patient's Diary. At Visit 3 (Week 4, Day 29), the patient should return all used and unused study drug packagings. The Investigator will check compliance with the recommendations for study drug self-administration at Visit 3 (Week 4, Day 29) based on the results of accounting for the returned study drug and the patient's diary.

The study drug compliance will be calculated at Visit 3 using the formula:

Compliance = (N dispensed. – N returned.) / N calc. * 100%

where N dispensed. = number of tablets/capsules dispensed, N returned. = number of tablets/capsules returned, N calc. = estimated number of tablets/capsules the volunteer was to receive since the previous visit.

The calculated percentage compliance will be categorized as:

- Too Low: < 80% compliance.
- Adequate: $\geq 80\%$ to $\leq 120\%$ compliance.
- Too High: > 120% compliance.

Sum dose of study drug (mg), duration of taken study drug (days) and average dose taken per day (mg) will be calculated for each subject. Data is collected in **patient diaries**.

Duration of taken study drug (days) will be calculated as sum of days where at least one dose were taken by subject.

Average dose taken per day (mg) will be calculated with the following formula:

Average dose taken per day (mg) = $\frac{\text{Sum dose of study drug (mg)}}{\text{Duration of taken study drug (days)}}$

All data of drug accountability, treatment compliance and exposure will be presented in subject data listings and by-treatment group tables.

4.3.11 Compliance with selection criteria assessments.

Source: NSL006, NSL007, NSL008, NSL009

Pregnancy test, test for HIV, hepatitis B and C, feces analysis for fecal calprotectin and colonoscopy results will be listed only.

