5.3. Compliance of the therapy conduction

The patient should take the first study drug dose at the Visit 2 day (Week 0). During telephone contact (TC 1, Week 2, Day 0), the Investigator checks the patient's treatment compliance and whether he/she follows the recommendations on the Patient's Diary filling, and, if necessary, conducts an additional conversation with the patient about the proper drug administration and filling out the Patient's Diary. At Visit 3 (Week 4, Day 29), the patient should return all used and unused study drug packagings. The Investigator will check compliance with the recommendations for study drug self-administration at Visit 3 (Week 4, Day 29) based on the results of accounting for the returned study drug and the patient's diary.

The study drug compliance will be calculated at Visit 3 using the formula:

Compliance = (N dispensed. - N returned.) / N calc. x 100%

where N dispensed. = number of tablets/capsules dispensed, N returned. = number of tablets/capsules returned, N calc. = estimated number of tablets/capsules the volunteer was to receive since the previous visit.

The compliance should be within the interval from 80% to 120%.

Confidential Page 51 of 94

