5.4. Packing and labeling of the study drugs

The study drug will be packed and marked in accordance with current law and applicable regulatory requirements, in particular, Federal Law # 61-FZ On Circulation of Pharmaceutical products" dd. April, 12 2010.

Label of investigational product is below:

Label of blister (Label 5829-L01)

Protocol no. MESI3001

Kit number: XXXXXX

Packaging batch number: 5829-BB

Tablet batch number: zzzzz

Contents: 10 film-coated tablets Mebeverine+Simethicone, 135 mg+80 mg

Sponsor: Abbott Product Operations AG

Label of secondary pack (Label 5829-L02)

Kit numb	er: XXXXXX
Instruction	ns for use and route of administration: oral use, 1 tablet 3 times a day, before meal
Packaging	g batch number:
Tablet bat	ch number: zzzzz
Not to be	used after: MM/YYYY
Contents:	100 tablets (10 blisters with 10 tablets Mebeverine+Simethicone, 135 mg+80 mg each)
Storage co	onditions: store in a light-protected place at a temperature not above 25°C
Sponsor: A	Abbott Product Operations AG
CRO:	

For registered medication Duspatalin® in standard trade package and standard label additional label will be applied:

Confidential Page 52 of 94

Label of blister (Label 5829-L03)

Protocol no. MESI3001

Kit number: XXXXXX

Packaging batch number:

Contents: 10 tablets Duspatalin® 135 mg

Abbott Product Operations AG

Label of secondary pack (Label 5829-L04)

FOR CLINICAL TRIAL USE ONLY

Protocol no. MESI3001

Kit number: XXXXXX

Instructions for use and route of administration: oral use, 1 tablet 3 times a day, before meal

Packaging batch number:

Not to be used after: MM/YYYY

Contents: 5 blisters with 10 tablets Duspatalin® 135 mg

Storage conditions: at a temperature below $30^{\circ}\mathrm{C}$

Abbott Product Operations AG

CRO:

KEEP OUT OF THE REACH AND SIGHT OF CHILDREN

For registered medication Espumizan® in standard trade package and standard label additional label will be applied:

Label of blister (Label 5829-L05) (simple white label)

Protocol no. MESI3001

Kit number: XXXXXX

Packaging batch number:

Contents: 25 capsules Espumisan® 40 mg

Abbott Product Operations AG

Confidential Page 53 of 94

Label of secondary pack (Label 5829-L06) (simple white label)

FOR CLINICAL TRIAL USE ONLY
Protocol no. MESI3001

Kit number: XXXXXX

Instructions for use and route of administration: oral use, 2 capsules 3 times a day, after or before meal

Packaging batch number:
Not to be used after: MM/YYYY

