5.5. Accounting of the study drug

KEEP OUT OF THE REACH AND SIGHT OF CHILDREN

The Investigator will be responsible for proper accounting registration of the study drugs to provide their proper receiving, storage, distribution and return. The patients will be instructed to return all, both used and unused, packages of the study drugs to the investigational site at Visit 3. The returned materials will be checked, assessed the patient's compliance. In case the patient loses the study drug package, an appropriate note should be written in the source documentation and in the study drugs accountability log.

Upon completion of the study, all remaining study medications (Mebeverine+Simethicone, Duspatalin®, Espumisan®) should be returned to the local depot and destroyed.

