7.4. Unscheduled visits

At the discretion of the Investigator, the patients may be invited for an unscheduled visit at any time in the course of the clinical study for safety reasons, in case a re-examination or repeated procedure is required, or to provide additional quantity of the study drug. During unscheduled visits, the Investigator may conduct the necessary procedures. Unscheduled visits should be registered in the source documentation and CRF. Unscheduled visits should not affect the schedule of planned visits provided by the Protocol of this clinical study

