Test / Examination	Visit name	Visit Label	Visit Number	Reference Start Date/Time	Relative Day Number
	Visit 1	Visit 1 (week 0)	2	Date of first Drug Administration	1
	Visit 2 (Telephone Call)	Visit 2 (Telephone Call)	3	Date of Telephone Call	15 (+-1)
	Visit 3 (End of Trial)	Visit 3 End of Trial or Early Discantinuation visit	4	Date of last Drug Administration	29 (+-1)
	Screening	Screening	1	Date of Informed consent obtained	-217
Flatulence intensity on the NRS-11 scale	Visit 1	Visit 1 (week 0)	2	Date of first Drug Adminitration	1
	Visit 2 (Telephone Call)	Visit 2 (Telephone Call)	3	Date of Telephone Call	15 (+-1)
	Visit 3 (End of Trial)	Visit 3 End of Trial or Early Discantinuation visit	4	Date of last Drug Administration	29 (+-1)
Stool frequency	Screening	Screening	1	Date of Informed consent obtained	-217
	Visit 1	Visit 1 (week 0)	2	Date of first Drug Adminitration	1
	Visit 2 (Telephone Call)	Visit 2 (Telephone Call)	3	Date of Telephone Call	15 (+-1)

Test / Examination	Visit name	Visit Label	Visit Number	Reference Start Date/Time	Relative Day Number
	Visit 3 (End of Trial)	Visit 3 End of Trial or Early Discantinuation visit	4	Date of last Drug Administration	29 (+-1)
Bristol stool scale	Screening	Screening	1	Date of Informed consent obtained	-217
	Visit 1	Visit 1 (week 0)	2	Date of first Drug Adminitration	1
	Visit 2 (Telephone Call)	Visit 2 (Telephone Call)	3	Date of Telephone Call	15 (+-1)
	Visit 3 (End of Trial)	Visit 3 End of Trial or Early Discantinuation visit	4	Date of last Drug Administration	29 (+-1)
Patient diary distribution	Screening	Screening	1	Date of Informed consent obtained	-217
	Visit 1	Visit 1 (week 0)	2	Date of first Drug Adminitration	1
Patient diary assessment	Visit 1	Visit 1 (week 0)	2	Date of first Drug Adminitration	1
	Visit 2 (Telephone Call)	Visit 2 (Telephone Call)	3	Date of Telephone Call	15 (+-1)
	Visit 3 (End of Trial)	Visit 3 End of Trial or Early Discantinuation visit	4	Date of last Drug Administration	29 (+-1)

Test / Examination	Visit name	Visit Label	Visit Number	Reference Start Date/Time	Relative Day Number
Evaluate the quality of life (IBSQOL questionnaire)	Visit 1	Visit 1 (week 0)	2	Date of first Drug Adminitration	1
	Visit 3 (End of Trial)	Visit 3 End of Trial or Early Discantinuation visit	4	Date of last Drug Administration	29 (+-1)
Study drug dispense	Visit 1	Visit 1 (week 0)	2	Date of first Drug Adminitration	1

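### The compliance formula counts lost or unreturned study drug as taken, so a non-adherent patient who loses or keeps leftovers can be classed Adequate

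*SAP*

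**What the plan says.** Protocol 5.3 gives the formula as "Compliance = (N dispensed. - N returned.) / N calc. x 100", and SAP 4.3.10 repeats it. The denominator is defined as "N calc. = estimated number of tablets/capsules the volunteer was to receive since the previous visit". The timing is a single calculation: "The study drug compliance will be calculated at Visit 3 using the formula". Protocol 5.3 adds that "The compliance should be within the interval from 80% to 120" per cent. The SAP turns this into three categories: Too Low below 80%, Adequate from 80% to 120%, and Too High above 120%.

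On lost drug, Protocol 5.5 says "In case the patient loses the study drug package, an appropriate note should be written in the source documentation", and the same note goes into the accountability log. Neither document carries that information into the formula. Used and unused packs are to be returned at Visit 3, or at the early discontinuation visit (Protocol 5.3, 5.5 and 7.5).

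On the diary, both documents have the investigator check compliance against returned drug and the diary. SAP 4.3.10 derives total dose, duration and average daily dose from the diary, but the compliance percentage does not use it.

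On visits, Protocol 7.2 and SAP 4.3.10 place first dosing at Visit 2 (Week 0), treat the Day 15 contact as a telephone contact, and end at Visit 3. SAP 6.1.5 calls randomization Visit 1 and labels the Day 15 call "Visit 2 (Telephone Call"). Protocol 7.4 allows unscheduled visits for safety, for repeat procedures "or to provide additional quantity of the study drug".

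**The concern.** A pill count measures intake only if every unit not taken comes back or is otherwise accounted for. The plan foresees that some will not, has the loss written down, and then computes a percentage that ignores it. The error runs in one direction: each missing unit raises apparent compliance. The upper limit of 120% is the only thing that could expose a patient who returns nothing, and the labelled pack sizes leave too little surplus for it to do so reliably.

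Non-return is also foreseeable beyond simple loss. Protocol 6.15 lets home visits or telemedicine replace site visits during the pandemic, while the drug is due back at Visit 3.

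The second issue is wording. A denominator that starts at the previous visit is safe only if everyone agrees which visit that is, and the two numbering schemes in the SAP do not agree.

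At stake are the compliance table and the information available at the blind data review, which decides exclusions from the Per Protocol sample. The PP analysis is sensitivity analysis 1 of the primary endpoint.

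**Working it through.** The documents state no computed compliance figure, so there is nothing to reproduce. The check applies their formula and band to their pack sizes and schedule.

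**Inputs from the documents**
- Daily units: 3 tablets (combination, Duspatalin) or 6 capsules (Espumisan); Protocol 5.2.
- Dosing days: first dose on Day 1, last dose the evening before Visit 3 (Day 29), so 28 days. The Visit 3 window of ±1 day gives 27 to 29.
- Scheduled units over 28 days: 28 × 3 = 84 tablets; 28 × 6 = 168 capsules.
- Pack sizes (Protocol 5.4): combination "100 tablets (10 blisters with 10 tablets Mebeverine+Simethicone, 135 mg+80 mg each"); Duspatalin 50 tablets; Espumisan 25 capsules.

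**Assumption.** Units dispensed per patient are not stated. I take the fewest whole packs that cover 28 days: combination 1 × 100, Duspatalin 2 × 50 = 100, Espumisan 7 × 25 = 175. Eight Espumisan packs (200 capsules) are shown as a variant.

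**Step 1: nothing returned.** Compliance = (dispensed − 0) / N calc × 100, regardless of true intake.

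| Arm | Dispensed | 27 days | 28 days | 29 days |
|---|---|---|---|---|
| Combination, Duspatalin | 100 | 100/81 = 123.5% (Too High) | 100/84 = 119.0% (Adequate) | 100/87 = 114.9% (Adequate) |
| Espumisan | 175 | 175/162 = 108.0% (Adequate) | 175/168 = 104.2% (Adequate) | 175/174 = 100.6% (Adequate) |
| Espumisan, variant | 200 | 200/162 = 123.5% (Too High) | 200/168 = 119.0% (Adequate) | 200/174 = 114.9% (Adequate) |

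**Step 2: partial intake, partial loss.** A tablet patient takes 42 of 84, a true 50%. If all leftovers come back, the score is 42/84 = 50%, Too Low, which is correct. The Adequate band starts at 0.80 × 84 = 67.2 tablets. With 25 tablets missing the score is 67/84 = 79.8%, Too Low. With 26 missing it is 68/84 = 81.0%, Adequate.

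**Step 3: the denominator on the natural reading.** Under Protocol 7.2 and the text of SAP 4.3.10, the visit before Visit 3 is Visit 2, when drug is dispensed. N calc is then 84, and a fully adherent patient who returns the remaining 16 of 100 tablets scores (100 − 16)/84 = 100%. There is no distortion.

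**Step 4: after the fix.** With documented losses subtracted, a patient who took nothing and lost all 100 tablets scores (100 − 0 − 100)/84 = 0%, Too Low. The half-course patient whose other 58 tablets are logged as lost scores (100 − 0 − 58)/84 = 50%, Too Low. The adherent patient still scores 100%.

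**The case against.** The strongest reply is that this is the ordinary limitation of pill counts. Return of all packs is required, and a non-adherent patient who complies with that is classed correctly. Lost packs are logged, and diary-based exposure is tabulated separately, so the data review can see a discordant case. A pill count beside an independent diary measure is a cross-check, and disagreement between the two is informative. Within the visit window, non-return can even be flagged: 123.5% at 27 dosing days in the tablet arms. All of this stands, and it limits the size of the point. It does not remove it, because the formula as written gives a known wrong answer in a situation that the protocol itself anticipates.

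A reader might infer more from the denominator, namely that adherent patients will be classed Too High. If the SAP 6.1.5 label made the Day 15 call the previous visit, N calc would be 14 × 3 = 42 and an adherent patient would score 84/42 = 200%. If an unscheduled visit on Day 6 counted, the score would be 84/69 = 121.7%. The documents do not support either as the intended rule. SAP 4.3.10 fixes its own sequence (Visit 2 at Week 0, telephone contact, Visit 3), and Protocol 7.4 says unscheduled visits are not to affect the planned schedule. What remains is an ambiguity worth closing.

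A reader might also infer that the diary should replace the pill count. That would exchange one bias for self-report in an open-label trial, and the documents give no reason to prefer it.

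**Conclusion.** The point holds in a limited form. The stated formula counts every lost or kept unit as taken, so a non-adherent patient who does not return leftovers can be classed Adequate. For a patient who returns nothing, the score at 28 dosing days is 119.0% in the tablet arms and 104.2% for Espumisan, at any true intake. These figures rest on the assumed smallest whole-pack supply. In the tablet arms they also depend on the visit window, since at 27 days the patient is Too High. Patients who return all leftovers are classed correctly. The number of patients affected cannot be derived from the documents.

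The previous-visit wording is a separate, minor ambiguity that does no harm on the natural reading.

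It would be tempting to conclude that the PP sensitivity analysis, or even the primary result, is biased. The documents do not show this. The primary analysis uses the FA sample and compliance does not enter the ANCOVA. No text makes the 80% to 120% band an automatic PP exclusion; SAP 4.1 leaves significant violations to the blind data review, where other information is also available. The effect is confined to the compliance table and to what that review has before it.

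**What to change.** In SAP 4.3.10:

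- **Numerator:** units dispensed at all visits, minus units returned, minus units documented as lost.
- **Unreturned packs:** class the pill count as not evaluable when packs are not returned. Protocol 5.5 asks for a note of a loss but not for a count, so a loss can be subtracted only where the number of units is recorded.
- **Denominator:** replace the reference to the previous visit with units scheduled from first dose to the last scheduled dose before Visit 3 or early discontinuation. This also settles the conflict with the labels in SAP 6.1.5 and the handling of unscheduled resupply.
- **Cross-check:** report a diary-based percentage, using the same denominator, beside the pill count and without replacing it.

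The cost is a few lines of SAP text and minor programming, since diary intake is already collected and used for exposure. Some patients will become not evaluable on the pill count. Protocol 5.3 carries the same formula, so the change should be identified as Protocol 9.10 requires. It should be settled before the blind data review.
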